1.4 Role of the Funder

The funder has reviewed the research protocol but will have no role in data collection, analysis, data interpretation, report writing or in the decision to submit the report for publication. The funder has approved the selection of members for oversight committees.

1.5 Protocol amendments

Version	Date	Summary of amendments
1.0	01.12.2020	N/A
2.0	26.04.2021	
Points of clarification:
 
• Details of REC, REC reference and ISRCTN registration added• correction to fibroid classification (type 0, 1, 2) 
Eligibility screening: Simplification of eligibility screening to a more pragmatic approach (2D ultra sound, as used by many sites, may be used to diagnose and measure fibroids and polyps in the assessment of eligibility).
 
Inclusion/exclusion criteria:

		
 • modification of inclusion criteria 2 to include multiple fibroids and polyps amassing to 3cm or less in total. • removal of inverse inclusion criteria from list of exclusions (modification to exclusion criteria 1 and removal of exclusion criteria 2). 
Data collection:
 
 • Data collection window +2 weeks added for follow-up data collection time points. • Patient satisfaction questionnaire moved from 6-months post-hysteroscopy to +2weeks post-hysteroscopy. • Removal of hysteroscopy detail and patient cost data collection from control participants who withdraw from allocated treatment (decide to undergo hysteroscopy). 
Adverse events:
 
 • Expected Adverse event ‘placenta accreta’ expanded to include placenta, increta and percreta • Placenta abruption added as an expected adverse event • Removal of ‘pain post procedure’ as a specific procedure related expected adverse event – this will be a symptom of other expected events listed e.g. injury, bleeding, haemorrhage, infection etc.
3.0	12.07.2021	
Co-applicant details change for [name]
 
Secondary Outcomes:
 
 • Addition of COVID-19 vaccination status (1st, 2nd, booster, approximate date and type of vaccine) • Update of Table 2 to reflect data fields that will be collected, as per section 8.1. 
Statistics – subgroup analyses Amended to explain that a sub-group analysis, looking at interaction between treatment group and fibroid type, may be carried out if said data is available for a sufficient number of control patients.

4.0	Not issued	Not issued
5.0	11.11.2021 (CURRENT)	
The trial is now registered on the NIHR Associate PI scheme Reference to Associate PI/Doctors added throughout.
 
1.1 Administrative changes
 
2.1 Background and rationale

	
Removal of references to studies related specifically to unexplained fertility in section 2.1 to remove any ambiguity in relation to the study population.
 
3.2 Objectives Removal of reference to unexplained fertility in the main trial objectives to ensure the objectives reflect the inclusion criteria.
 
4 Trial Design Updated time frames due to potential impact of COVID-19 on the planned 2.5 year recruitment window. Removal of Gantt chart.
 
5.1 Inclusion criteria Replacement of 'women of reproductive age' with 'women seeking fertility treatment', as the former infers age restrictions for recruitment.
 
Addition of statement to clarify that women with known and unknown causes of infertility can be recruited, as intended.
 
5.3 Patient identification pathways Note added to clarify identification of patients in initial phase ART and ovulation induction.
 
6.1 Patients randomised to intervention group Paragraph added under heading 'Misdiagnosis' outlining course of action that should be taken.
 
7.0 Randomisation and enrolment Addition of back-up randomisation plan in the event SCRAM is unavailable.
 
11.1 Sample size and 11.2 Statistical analysis Addition of clinical pregnancy outcome as a proxy or surrogate outcome for the primary outcome (live birth rate) in the interim analysis, in order to inform a decision to alter the sample size of one or both of the trials.

--	--------------------------------------------------------------------------------------------------------------------------------------------------------------------------------------------------------------------------------------------------------------------------------------------------------------------------------------------------------------------------------------------------------------------------------------------------------------------------------------------------------------------------------------------------------------------------------------------------------------------------------------------------------------------------------------------------------------------------------------------------------------------------------------------------------------------------------------------------------------------------------------------------------------------------------------------------------------------------------------------------------------------------------------------------------------------------------------------------------------------------------------------------------------------------------------------------------------------------------------------------------------------------------------------------------------------------------------------------------------------------------------------------------------------------------------------------------------------------------------------------------------------------------------------------------------------------------------

Trial Summary

Study title	HELP Fertility?
Sponsor	Sheffield Teaching Hospitals NHSFT
Funder	National Institute of Health Research, Health Technology Assessment (NIHR, HTA)
ISRCTN	91356224
Project start date	April 2020
Project end date	October 2028
Hypothesis, aims and objectives	
What is the clinical and cost-effectiveness of hysteroscopic removal of submucosal fibroids and endometrial polyps compared to no hysteroscopic removal, in women presenting with infertility and recurrent miscarriage?
 
A) Assess the feasibility of conducting two multi-centre RCTs of hysteroscopic resection of endometrial polyps and submucous fibroids in women suffering from infertility or recurrent miscarriage, by conducting two RCT internal pilots; one for women with endometrial polyps and one for women with submucous fibroids;
 
B) If feasible, determine the clinical and cost-effectiveness of the hysteroscopic removal of endometrial polyps and submucosal fibroids to improve fertility in women suffering from infertility or recurrent miscarriage;
 
C) To determine patient experience and satisfaction, procedure related complications;
 
D) To assess the long-term effect of hysteroscopic resection of endometrial polyps

	and submucous fibroids, by collecting and analysing routinely collected NHS data.
Trial design	
An “Umbrella” RCT with two concurrent pragmatic, open, multi centre RCTs.
 
Both trials involve 1:1 randomisation, hysteroscopic resection vs no hysteroscopic resection

Internal pilot criteria	
Targets at 9 months; 30 centres set-up and recruited first participant
 
Fibroid RCT: Average of 0.67 participants recruited per centre per month (approx. 117 participants recruited in total)
 
Polyp RCT: Average of 1.3 participants recruited per centre per month (approx. 227 recruited in total)
 
Withdrawal from control treatment: 0% of control participants received intervention before 6 months post randomisation
 
Intervention waiting times: 100% of participants randomised to the intervention (resection of fibroids or polyps) receiving the treatment before 3 months post-randomisation.
 
Detailed green/amber/red criteria for both RCTs are included in section 8.1

Setting	Secondary and tertiary fertility or gynaecology units providing care for women with infertility and recurrent miscarriage

Participants	
Inclusion criteria;
 
1) History of primary or secondary infertility or recurrent miscarriage, as defined in section 5.12) Diagnosed endometrial polyps or submucosal fibroids 3 cm or less in size (or amass to 3cm or less in total) 
Exclusion criteria;
 
1) The presence of additional medical morbidity as a result of the submucous fibroid or endometrial polyp such as anaemia due to heavy periods or significant pain which necessitates surgical intervention2) Asherman's syndrome3) Malignancy of endometrial polyp/submucous fibroid is suspected4) The patient is taking part in any other interventional infertility trial5) Pregnancy, or pregnancy is suspected.6) Previously randomised into the other trial (RCT 1 and RCT2)
Intervention & control groups	
Intervention group: hysteroscopic removal of submucous fibroids and / or endometrial polyps.
 
Control group: no hysteroscopic removal of submucous fibroids and / or endometrial polyps.

Primary outcome(s)	Live birth rate (LBR) at 15 months post-randomisation
Secondary outcome(s)	
- LBR at 24 months post-randomisation- Time from randomisation to live birth- Time from randomisation to pregnancy

	
 - Clinical pregnancy, miscarriage, premature labour, multiple birth, still birth and ectopic pregnancy rates - Detail of hysteroscopy received - Patient satisfaction - Details of fertility treatments received, including details of medications received and assisted reproductive techniques received - Incorrect diagnosis/absence of abnormalities at surgery - Type of submucous fibroid (type 0, 1, or 2). - Number of participants randomised to the control arm (no resection of fibroids or polyps) who receive the treatment (resection) before 6 months post-randomisation. - Number of participants randomised to the intervention (resection of fibroids or polyps) who receive the treatment before 3 months post-randomisation. - Adverse events (procedure related and gynaecological/obstetric related complications) (refer to section 10) - Health resource use and patient cost - Cost per live birth gained 
Long term outcomes (minimum 5 years post randomisation):
 
 - Live birth rate - miscarriages, terminations and still births - details of fertility treatments - details of hysteroscopy received

Duration of recruitment period and first enrolment date
	
Duration of recruitment period: 2 years and 6 months (pre-COVID-19 pandemic plan)

	First enrolment date for the pilot phase will be July 2021
Duration of follow-up	Minimum of 24 months post-randomisation (participants to be followed up to the last participant completing the 24-month data collection) Long-term follow up at least 5 years post randomisation
Target sample size	1120
Definition of end of trial	Completion of the 24-month follow-up by the last participant recruited (last patient last visit, LPLV)

2. Introduction

2.1 Background and rationale

Uterine fibroids remain the commonest benign tumours of the female genital tract affecting 20-40% of women in the reproductive years and are commonly encountered in women undergoing fertility treatment (1). Intracavitary fibroids have been reported in around 5-18% of patients with infertility and about 7% of women with unexplained infertility (2,3). There is evidence, largely from observational studies, that submucous fibroids may have a negative effect on reproductive performance (4) by both distorting the endometrial cavity and possibly disrupting subendometrial blood flow (5). Surgical removal of these fibroids in order to improve reproductive performance has become widely accepted practice (6), despite the existing evidence to support the resection of fibroids coming largely from small observational studies with a clear lack of good quality randomised controlled trials (6,7).

Endometrial polyps are also a common finding, occurring in an estimated 11-45% of women undergoing in vitro fertilisation and 15-25% of women with unexplained infertility (2,8,9). Endometrial polyps may have a negative effect on fertility as evidenced by a negative effect on markers of endometrial receptivity such as HOXA10 and HOXA11 mRNA levels (8). Based on the assumption that these polyps can adversely affect reproductive performance, hysteroscopic removal, similar to submucous fibroids, has become a popular intervention in women with fertility problems despite the fact that this practice is not yet supported by a body of evidence from randomised controlled trials (10). Most of the studies that have examined the effect of endometrial polyps on pregnancy rates were small observation non-controlled studies (10–19) and, amongst these studies, there is controversy regarding whether or not they have a negative effect on conception rates. This suboptimal quality and conflicting nature of the evidence was highlighted in a 2010 systematic review (20). The most recent meta-analysis has shown an increase in clinical pregnancy rates after hysteroscopic resection of fibroids after intrauterine insemination but not after In Vitro Fertilisation (IVF) and has highlighted the importance of more randomised controlled trials (21).

Hysteroscopic removal of polyps and fibroids is not without risks, some of which, such as uterine perforation, Asherman's Syndrome and intrauterine adhesions, may have a negative effect on fertility (22,23). Surgery poses a significant economic burden on an already burdened National Health Service (NHS), and can cause the patient significant anxiety, affecting pain perception and satisfaction (24).

Due to the poor quality of the existing evidence and as highlighted by the National Institute for Health and Care Excellence (NICE), Health Technology Assessment (HTA) brief and the Cochrane review (6,25), further research is needed to determine whether hysteroscopic removal of these uterine cavity abnormalities is beneficial; not only in increasing the live birth rates to help inform and guide practice but also in relation to the significant economic burden placed on the NHS by performing a procedure with inadequate evidence (1).

Currently hysteroscopic removal of submucous fibroids and endometrial polyps is being routinely performed in the NHS for women with infertility including those where no particular other impediment to fertility can be found (unexplained infertility) and women with recurrent miscarriage. This is despite NICE guidance stating that the effectiveness of surgical resection has not been established (25). The procedure poses a significant cost to the NHS. In addition, surgery carries risks, some of which may cause further detriment to fertility and costs to the NHS – these risks include uterine perforation, fluid intravasation and Asherman's syndrome (6,29).

If resection of fibroids and polyps does indeed improve reproductive performance, then this would have a potential influence on existing fertility pathways. For example, the NICE guidelines for fertility management suggest that IVF is the optimum treatment for women with unexplained infertility (25). Funding for IVF however is variable and inconsistent across the UK and is often limited to a single cycle. If women with submucous fibroids or polyps associated with unexplained infertility were to benefit from resection of these lesions, then in many cases IVF treatment could be avoided with consequent cost savings to both the NHS and to self-funding patients.–There is a current trend towards local authorities reducing funding for fertility treatments, thus increasing the burden on patients to fund this treatment themselves. Given this, and the emotional and medical side effects of receiving such treatments, it is imperative that evidence is created to guide clinicians and patients on the effects of hysteroscopic resection so that they can make an informed decision in relation to the patient's chances of live birth (30). There is therefore a current urgent need for a well-designed definitive study examining the effect of hysteroscopic resection of submucous fibroids and polyps in the two distinct populations of women with infertility and women with recurrent miscarriage, whether being managed expectantly or with active fertility interventions.

3. Aims and objectives

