10.2 Recording and reporting

AEs and SAEs are defined as an event that occurs after the patient has provided written informed consent for trial entry and up to completion of the 24 month follow-up by the last participant recruited (LPLV).

Hysteroscopic resection of submucous fibroids and endometrial polyps is a routine procedure for which the side effects are understood. Therefore, only those AEs which are deemed serious or of particular relevance to the procedure will be recorded / reported in this trial. These are listed as 'expected AEs' in Table 4.

Adverse Events

Participants will be asked for any details of adverse events, at four time points up to the participants' final study related follow-up event; post procedure (if randomised to receive hysteroscopic resection of submucous fibroids or endometrial polyps), then at 6, 15 and 24 months post randomisation. AEs or SAEs may also be identified by the Research Nurse/Associate PI/Dr, or any other individual, at any point during the study, up to last patient last visit.

When an event is identified the process for recording and reporting outlined in Figure 5 will be followed. The local PI (or other suitably trained member of research staff, if the task is delegated to them) should be notified immediately and assess the event for classification as an SAE (see definition in section 10.1).

AEs confirmed as NOT serious will be checked against the list of expected AEs (Table 4).

Expected AEs

AEs which are expected will be recorded by site staff in the participant CRF.

Unexpected AEs

AEs which are not expected will not be recorded on the basis that hysteroscopic resection of submucous fibroids and endometrial polyps is a routine procedure, for which the side effects are understood. We do not anticipate any AEs, which are of relevance to the intervention, other than those listed in Table 4, unless the site PI considers the events to be significant.

Sites are asked to enter all available information onto the study database as soon as possible after the site becomes aware of the event.

Table 4 - Expected Adverse Events

Gynaecological / obstetric related	Procedure related (immediate)	Procedure related (delayed)

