
● Placenta accreta, increta, percreta● Placenta abruption● Growth retardation● Foetal distress● Antepartum haemorrhage● Post-partum haemorrhage● Placenta Praevia (grade 3 & 4)● Placental abruption● Manual removal of placenta	
● Uterine perforation● Bowel injury● Bladder injury● Significant bleeding during the procedure resulting in additional intervention● Air embolism (though this is very rare and more commonly associated with resection of Type 2 submucous fibroids)● Fluid overload and hyponatremia● Vasovagal reaction (hypotension and fainting) requiring additional intervention during the procedure (e.g. presence of anaesthetist) OR after the procedure● Return to theatre immediately	
● Post-operative adhesions requiring intervention● Infection

Serious Adverse Events

All AEs classed by the PI or delegate as serious will require more detailed information to be recorded in the participant CRF. In such cases, the event must also be reported to the Sheffield CTRU within 24 hours of the site becoming aware of the event (see section 10.4).

[figure not shown]
Expected Serious Adverse Events

Expected SAEs are those events listed in Table 4 which are assessed as serious using the definition in section 10.1.

Unexpected Serious Adverse Events

All unexpected serious adverse events should be assessed for causality by the PI or delegate. Following reporting of these events within 24 hours by site staff to the CTRU, all unexpected SAEs will be reported by the CTRU to the sponsor and DMEC. SAEs which are unexpected and related / suspected to be related to the intervention will be reported further by the CTRU to the REC within 15 working days.

Figure 5 - Recording and reporting of AEs and SAEs

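### Table 4 records adhesions only if they require intervention, although the rationale names adhesions and Asherman's syndrome, with no threshold, as surgical risks to fertility

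*Protocol*

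**What the plan says.** **Rationale (Protocol Section 2.1).** The protocol says that removal carries risks, and that some of them, including uterine perforation, Asherman's syndrome and "intrauterine adhesions, may have a negative effect on fertility". A later paragraph of the same section, on possible further detriment to fertility and cost, says that "these risks include uterine perforation, fluid intravasation and Asherman's syndrome". Neither list ranks the harms or limits them to cases that need treatment.

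**Recording rule (Section 10.2).** Because the procedure is routine, "only those AEs which are deemed serious or of particular relevance to the procedure will be recorded / reported in this trial"; the section says these are the events listed in Table 4. For non-serious events outside the table, "AEs which are not expected will not be recorded". The reason given is: "We do not anticipate any AEs, which are of relevance to the intervention, other than those listed in Table 4". A closing clause makes an exception for events that the site PI considers significant.

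**Table 4.** Among immediate procedure-related events it lists "Uterine perforation" with no qualifier. The delayed column has two entries: infection, unqualified, and "Post-operative adhesions requiring intervention". Asherman's syndrome does not appear by name.

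**Where the data are used.** Procedure-related complications are part of main objective C (Section 3.2) and are outcome 13 (Section 8.3). Section 11.2 compares adverse events between the randomised groups with a test and a 95% confidence interval.

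**The concern.** The rationale and the recording rule do not match. Section 2.1 treats adhesions and Asherman's syndrome as risks that may reduce fertility, whether or not anyone acts on them. Section 10.2 justifies its restriction by saying that nothing relevant is expected outside Table 4, yet Table 4 covers only part of what Section 2.1 names.

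The group that can be lost is women with adhesions diagnosed at a later scan or hysteroscopy, not serious, and judged not to need intervention. What the trial would report under objective C is then the rate of adhesions judged to need intervention. In a fertility trial a reader may take it for the adhesion rate. If live birth does not improve after resection, a low count could wrongly suggest that adhesions played no part.

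The definition drives what sites enter on the case report form. A later analysis plan cannot recover events that were never recorded.

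**Working it through.** **1. Rationale against recording rule**

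| Harm named in Section 2.1 | Entry in Table 4 | Threshold |
|---|---|---|
| Uterine perforation | Listed (immediate) | None |
| Fluid intravasation | Listed as fluid overload and hyponatraemia (immediate) | None |
| Intrauterine adhesions | Listed (delayed) | Must require intervention |
| Asherman's syndrome | Not named | Recorded only as far as the adhesions entry covers it |

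Of the fertility-related harms, only adhesions carry a threshold, and only Asherman's syndrome is not named.

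**2. Other routes by which such a case could be recorded**

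- Post-hysteroscopy form (Section 9.1): asks about complications during the procedure. Adhesions sit in Table 4's delayed column.
- Secondary and long-term outcomes (Sections 8.3 and 8.4): adhesions are not among them. The hysteroscopy details named in outcome 6 are number of procedures, abstinence and type of resection, in the intervention arm only.
- Site PI significance clause (Section 10.2): can capture a case, at the discretion of staff who know the allocation (Section 7.1).
- Serious adverse event route (Section 10.1): an investigator may class an event as serious if medically significant. This is also a matter of judgement.
- Scheduled uterine assessment after resection: none is planned.

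So capture is possible outside Table 4, but it is discretionary and can differ between sites.

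**3. Size**

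The stated sample size supplies the number of women per arm. For 10% against 20%, two-sided 5% and 90% power, with pooled variance and no continuity correction:

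n = [1.96 × √(2 × 0.15 × 0.85) + 1.2816 × √(0.10 × 0.90 + 0.20 × 0.80)]² / 0.10² = 266 per group.

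532 / 0.95 = 560 per trial, or 280 per arm. This agrees with Section 11.1 and does not depend on the present point.

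The protocol gives no adhesion rate and no share requiring intervention, so the under-count cannot be derived. As an illustration on assumed values only:

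cases outside the Table 4 term = 280 × assumed adhesion rate × (1 − assumed share requiring intervention)

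| Assumed rate | Cases in 280 | Outside term if 10% require intervention | 25% | 50% | 75% |
|---|---|---|---|---|---|
| 2% | 5.6 | 5.0 | 4.2 | 2.8 | 1.4 |
| 5% | 14 | 12.6 | 10.5 | 7.0 | 3.5 |
| 10% | 28 | 25.2 | 21 | 14 | 7 |
| 20% | 56 | 50.4 | 42 | 28 | 14 |

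The span, about 1 to 50 per trial, is too wide to serve as an estimate. It also assumes that all 280 women are resected, that every adhesion is detected, and that neither discretionary route is used.

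**The case against.** The strongest reply is that the threshold looks deliberate. Table 4 uses the same device for bleeding and for vasovagal reactions, and Section 10.2 explains that recording is limited for a routine procedure with known side effects. That explains a restriction in general. It does not explain why an event the protocol itself links to fertility is limited in this way when perforation is not.

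A second reply is that nothing is excluded outright, because the PI clause and the serious-event route remain open. This stands as a limit on the point: such cases are unrecorded by default, not barred. Likewise, requiring intervention is not the same as being treated. Adhesions judged to need intervention but declined or still awaiting it fit the present term.

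A third reply is that rewording Table 4 cannot reveal undetected adhesions, since no uterine assessment follows resection, and that diagnosis will depend on who is investigated later. This also stands. It limits what the change can deliver but is no reason to discard cases that have been diagnosed.

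A reader might go further and infer that adhesions are the harm most relevant to the primary outcome. Section 2.1 does not rank them, and it names perforation in both lists. A reader might also infer that recording depends on whether the woman has conceived. That is conceivable, but the protocol says nothing to establish it.

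**Conclusion.** The mismatch between Section 2.1 and Table 4 is real and worth correcting. As written, objective C receives a partial adhesion count: those judged to need intervention, plus whatever sites choose to report through discretionary routes. The shortfall cannot be quantified from the protocol, and the illustrative range rests wholly on assumed rates.

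A reader might infer that the live birth result is compromised. The documents do not support this. Section 11.2 analyses all randomised women by allocation whatever happens afterwards, so any effect of adhesions on live birth is already inside the comparison. For the same reason, a projected loss of live births says nothing about recording. An example is 0.20 × 0.10 = 0.02, or 2 percentage points, if an assumed 10% of resected women had adhesions that prevented every birth. The primary estimate, the sample size and the primary analysis are unaffected. What is affected is one component of the safety outcome and the ability to interpret the main result.

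**What to change.** Reconcile Table 4 with Section 2.1. Replace the adhesions entry with intrauterine adhesions or Asherman's syndrome diagnosed after randomisation, whether or not intervention is required. Record it in both arms, with the date of diagnosis and a flag for whether intervention was required. The flag lets the present Table 4 definition be reported as a subset, so nothing is lost. Report the count in each arm beside the number of women who had a later uterine assessment.

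The cost is one changed table line and a short case report form item, plus the count of women assessed later. Adverse events are already asked about at 6, 15 and 24 months, so no visit or procedure is added and clinical care does not change. The downside is that only diagnosed cases are recovered and that detection depends on who is assessed later, which may differ between arms. The reported denominator shows that limitation but does not remove it.
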